3.4 Sample size calculation

We aim to include 10 infants diagnosed with PAIS on MRI, who will be treated with MSCs via the nasal route.

Since this is a proof-of-principle study, the sample size is not only calculated based on expected power, but on the feasibility to be successful in recruitment of individuals needed for this study in order to complete the protocol in 2 years. It is expected that about 180,000 infants will be born alive per year.(StatLine 2015) Since the incidence of PAIS is 1/2300 there will be about 80 PAIS patients in the Netherlands yearly. A study from our group showed that about 26% of all PAIS patients involved the main MCA branch.(Harteman et al. 2012) Based

on this expectation, we think it will be feasible to recruit 10 PAIS patients in 12-24 months. We furthermore expect only a minimal drop out of initially included patients because PAIS is not life-threatening and follow-up is tightly regulated in all NICUs, including the WKZ.

Data analysis

Data will be analyzed on an intention to treat basis. SAEs are planned to be compared. Statistical analysis is described in detail in chapter 8.

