5.4 Summary of known and potential risks and benefits

An overview of findings on potential risks and benefits of MSC treatment for PAIS is given in chapters 7 and 8 of the IB.

In summary, we have shown in our own mouse models of neonatal ischemic infarction that intracerebral application of murine adult bone marrow-derived MSCs markedly improves outcome. Treatment with MSC reduced infarct size by >45%, stimulated formation of new neurons and oligodendrocytes, partially restored cortico-spinal motor tract activity, and improved sensorimotor outcome.(van Velthoven et al. 2010c; van Velthoven et al. 2010a) Additionally, our findings indicate that MSCs can be successfully and rapidly administered to the brain via an efficient non-invasive route, the nasal route.(Donega, van Velthoven, Nijboer, van Bel, et al. 2013) The MSCs subsequently accumulate predominantly in the infarcted area. Notably, MSCs delivered via the nasal route reduce infarct size and improve motor function to the same extent as MSCs administered intracranially.(van Velthoven et al. 2010b)

In general, risks or adverse events related to MSC treatment can be categorized in three groups: acute, subacute and longterm adverse events.

- 1. Acute adverse events: Administration Reaction/Toxicity
 - Systolic blood pressure >33% decrease or increase from the baseline during or directly following the intranasal administration of the investigational product
 - Diastolic blood pressure >25% decrease or increase from baseline during or directly following the intranasal administration of the investigational product
 - Heart rate >33% decrease or increase from baseline during or directly following the infusion of the investigational product
 - Development of dyspnoea, vomiting, flushing, diarrhea, during or within 1 hour from the intranasal administration of the investigational product
 - Fever ≥ 2 grade increase from baseline during or within 2 hours from the intranasal administration of the investigational product
 - Development of exanthema, or urticaria developing during or within 2 hours from the intranasal administration of the investigational product

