6.7 Premature termination of the study

The study may be terminated prematurely for safety or futility reasons if there are AEs or SAEs as defined by chapter 7.

We will use the following stopping rules:

- If the region of infarction, as defined on T2 weighted MR imaging and/or DWI, increases by >20% after treatment with MSCs in 3 different patients.
- If there appear to be any adverse effects that might be related to admission of MSCs in 3 different patients. These adverse effects include:
 - Systemic infections / meningitis
 - o Hemorrhagic transformation of the infarction
 - Gastrointestinal hemorrhage
 - o Thromboembolism
 - Formation of malignancies
- Unexpected and unaccountable deterioration of clinical situation, for example persistent seizures, after treatment with MSCs in 3 different patients. Usually, stroke-related seizures will disappear within three days following their onset and treated with anti-epileptic drugs.
- Mortality after treatment with MSCs in one patient will stop the study temporarily until an investigation has been performed.

Continuation of the study will only take place after the first three infants completed their second MRI scan at 3 months of age. This will safeguard that all stopping criteria will be monitored closely and the study may be terminated prematurely in time when stopping criteria are met.

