8. STATISTICAL ANALYSIS

In this study, 10 newborns will be included who will be treated with MSCs via the nasal route. This is a phase I/II, open-label, single-arm, single-center intervention study to assess the safety and feasibility of intranasal BM-MSCs in neonatal stroke patients.

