8.1 Study parameter(s)

Safety is defined primarily as the absence of treatment-related serious adverse events (SAEs) according to the Consolidated Standards of Reporting Trials (chapter 7.2 and bron), secondly as the absence of dose-limiting toxicity, defined as death within 24 hours after MSC transplantation or anaphylactic shock related to the MSC administration, and thirdly as the absence of adverse events at 3 months of age in terms of cerebral damage and neurodevelopmental outcome (see secondary outcome).

For acute safety, all vital signs and blood sample parameters (continuous variables) at baseline and at 24 hours following MSC transplantation will be compared using Wilcoxon signed-rank tests. The occurrence of SAE's, including mortality, toxicity, tumor growth, etc (see chapter 11.1) will be expressed in percentages and analyzed qualitatively.

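### For 24-hour vital signs and all blood values, section 8.1 plans only a group-level signed-rank test, which can miss large changes in a few infants and sets rises against falls

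*Combined protocol and SAP*

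**What the plan says.** The primary objective (section 1) is acute safety, and it names vital signs and blood sampling before and after treatment among the things to be assessed. Section 8 describes a single-arm study: "In this study, 10 newborns will be included who will be treated with MSCs via the nasal route". Section 8.1 then says that vital signs and "blood sample parameters (continuous variables) at baseline and at 24 hours following MSC transplantation will be compared using Wilcoxon signed-rank tests". It gives no significance level, sidedness, multiplicity rule, limit for a harmful change, listing or count of infants. Section 8.2 adds nothing.

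The next sentence of 8.1 says that SAEs, toxicity among them, will be given as percentages and analysed qualitatively, with a pointer to chapter 11.1. Chapter 11.1e, like section 5.4, lists limits that apply to the individual infant under the label of administration reaction or toxicity, for example "Systolic blood pressure >33% decrease or increase from the baseline during or directly following the intranasal administration". There are similar two-directional limits for diastolic pressure and heart rate, and a one-directional limit for fever. The blood-pressure and heart-rate limits apply during or directly after dosing, and the fever limit up to 2 hours after it. No per-infant limit is given anywhere for CRP, procalcitonin or blood count. Section 7.2.1 requires all adverse events to be recorded, but 8.1 reports only the serious ones.

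**The concern.** A signed-rank test asks whether the typical infant's value moved one way. Safety, as 6.1.1 and 8.1 define it, is the absence of events in individual infants, and the blood-pressure and heart-rate limits treat a rise and a fall alike as a reaction. The test does not fit that question in three ways:

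- A very large change counts only through its rank.
- One affected infant out of ten leaves almost no trace in the result.
- A large rise in one infant is set against a large fall in another.

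Because every parameter is tested and no multiplicity rule is given, some small p-values are also to be expected by chance.

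At stake is the acute-safety read-out of what the protocol describes as the first intranasal use of these cells in humans. The report could show a row of unremarkable p-values while several infants had changed sharply, or one chance p-value that draws attention for no reason.

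**Working it through.** **Inputs**

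- Pairs: 10 (section 8). Section 3.4 bases this number largely on recruitment feasibility and gives no power, effect size or SD.
- Dropout: section 3.4 says "We furthermore expect only a minimal drop out of initially included patients", with no figure. Taken as none; 9 and 8 pairs are checked as well.
- Test: signed-rank, baseline against 24 hours (8.1).
- Level and sidedness: not stated. Two-sided 5% is assumed, and other choices are shown.
- Number affected: the documents give no target, so one to six are shown. Three serves as a benchmark.

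The plan states no detection figure for this test, so there is none to reproduce.

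**Rejection region.** For n = 10 there are 2^10 = 1,024 equally likely sign patterns under no effect. At two-sided 5% the test rejects if the smaller rank sum is 8 or less, which has exact size 50/1,024 = 4.88%.

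**Three infants, same direction, changes as large as you like.** They hold ranks 8, 9 and 10, which sum to 27. The other seven are symmetric about zero and hold ranks 1 to 7, with 2^7 = 128 sign patterns. The test rejects only if the ranks with the opposite sign sum to 8 or less. The number of subsets of {1,…,7} with sums 0 to 8 is 1+1+1+2+2+3+4+5+5 = 24. Power is therefore 24/128 = 18.75%, and the miss rate is 81.25%.

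This is a ceiling on power. Simulated power with normal data was 9.6% for a 1 SD shift in the three, 15.7% for 2 SD, 18.3% for 3 SD, 18.8% for 5 SD and 18.7% for 100 SD.

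**Other levels, three affected**

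- One-sided 5% or two-sided 10%: the critical sum is 10. The subsets number 24 + 6 + 7 = 37, and 37/128 = 28.9%, so 71.1% are missed.
- Two-sided 1%: the critical sum is 3. The subsets number 5, and 5/128 = 3.9%, so 96.1% are missed.
- 9 or 8 complete pairs at two-sided 5%: 84.4% missed.

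**Number affected (n = 10, two-sided 5%)**

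| Infants affected | Power | Missed |
|---|---|---|
| 1 | 4.9% | 95.1% |
| 2 | 9.8% | 90.2% |
| 3 | 18.75% | 81.25% |
| 4 | 34.4% | 65.6% |
| 5 | 59.4% | 40.6% |
| 6 | 87.5% | 12.5% |

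With one infant affected, the rejection rate equals that under no effect.

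**Opposite directions.** Three large rises and three large falls occupy ranks 5 to 10. Either side then sums to at least 5+6+7 = 18, which exceeds 8, so rejection is impossible. If the three large changes are not all in one direction, power is 0% to 0.8%.

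**Drift in the other seven (simulated, three large changes).** Drift in the same direction of 0.2 or 0.5 SD raises power to 35% or 64%. Drift in the opposite direction lowers it to 8% or 2%.

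**Multiplicity.** Assume nine parameters: heart rate, two blood pressures, temperature, CRP, procalcitonin and three blood-count values. With no effect and independent tests, the chance of at least one p<0.05 is 1 − (1 − 0.0488)^9 = 36%. Positive correlation between parameters lowers it.

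**The case against.** The strongest reply is that the signed-rank test does not carry the safety conclusion. Safety is defined through treatment-related SAEs, then dose-limiting toxicity, then findings at 3 months. Stopping rests on clinical and MRI counts, and a DSMB watches throughout. Nowhere do the documents say that a non-significant p-value establishes acute safety. A reader might infer that it would be used that way, but the text does not support this. What remains is that the plan gives no other read-out for these data.

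A reader might also infer that the test is the only planned analysis of acute vital signs altogether. That is too broad. The SAE sentence in 8.1 points to chapter 11.1, where per-infant limits for blood pressure, heart rate and fever are listed as toxicity. The route is loose, however: the sentence covers serious events only, and the limits apply around dosing. It does not reach 24-hour values or non-serious exceedances, and blood values have no limit to which it could apply.

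Three further cautions stand:

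- The stopping rule "If there appear to be any adverse effects that might be related to admission of MSCs in 3 different patients" concerns listed clinical effects, and the other three-patient rules concern infarct growth and unexplained deterioration. None covers vital-sign or laboratory changes, so three is a benchmark here and not a detection target set by the protocol.
- Two-directional harm is written into the plan only for blood pressure and heart rate around dosing. For the blood values, whether both directions matter has still to be settled.
- The figures describe a paired single-arm test and do not carry over to a controlled comparison.

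**Conclusion.** The point holds for the 24-hour vital signs and all blood values: the one planned analysis addresses a group shift, and nothing in section 8 shows or counts individual infants. At an assumed two-sided 5% level, with 10 complete pairs, harm in one direction and no drift in the rest, a change of any size in 3 of 10 infants is missed at least about 81% of the time. The level and the number of pairs move the figure for an unlimited change between 71% and 96% without altering the conclusion. Drift in the other seven moves it more, to a miss rate of 36% with 0.5 SD in the same direction or 98% with 0.5 SD in the opposite direction. The 81% is therefore conditional and not a fixed property of the trial. The impossibility of rejecting with three large rises against three large falls needs only the 10 pairs and the assumed level.

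The multiplicity figure of 36% is the weaker part, since it rests on an assumed count of nine tests and on independence. It would be too strong to say that the trial's safety conclusion will be wrong. What is supported is that the planned read-out is poorly matched to the stated question and that a better one is cheap.

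**What to change.** In section 8.1:

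- For each vital sign and blood parameter, list every infant's baseline value, 24-hour value and change.
- Report the number of treated infants whose change exceeds a limit that the sponsor fixes in advance, in either direction where relevant, with an exact interval.
- Add a shift table against the laboratory's neonatal reference range.
- Give the median change with a Hodges-Lehmann interval as description. Label any Wilcoxon p-values as descriptive, and state that no p-value will be used to conclude safety.
- Tabulate non-serious exceedances of the 11.1e limits by infant, so that those limits are carried explicitly into section 8.

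The cost is a few more tables, agreement on limits for the blood values before the data are seen, and giving up the p-value as a read-out. The baseline and 24-hour measurements are already planned, so no new samples are needed.

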8.2 Other study parameters

Not applicable.

8.3 Interim analysis (if applicable)

No interim analysis will be performed. Stopping rules are described in chapter 6.7. A DSMB will be established to advice on stopping, as is described in chapter 7.5 and in the DSMB Charter.

9. ETHICAL CONSIDERATIONS

9.1 Regulation statement

This study will be conducted according to the principles of the Declaration of Helsinki (version 2013: www.wma.net) and in accordance with the Medical Research Involving Human Subjects Act (WMO) and other guidelines, regulations and Acts.

9.2 Recruitment and consent

Parents of neonates born in a Dutch hospital and/or admitted to our NICU who are potentially eligible for inclusion into the study will be informed as soon as possible after suspicion of PAIS about the study protocol by a neonatologist involved in the study. These parents include those of infants with or without symptoms of PAIS (*i.e.* one sided convulsions) and a PAIS confirmed with MRI. The parents will receive both the patient information letter describing the research proposal as well as an informed consent form. As soon as possible but allowing for an appropriate period of time allowing the parents to read, understand and, if necessary, having received additional information if requested, consent for participation will be asked in case PAIS (in the MCA region) is confirmed within 7 days after the onset of symptoms by MRI (including 3D-T1, T2 weighted, DWI and DTI sequences). Following written parental consent, patients will then be included in our study. Patients with PAIS that are diagnosed more than one week after birth are not eligible for enrolment.

9.3 Objection by minors or incapacitated subjects (if applicable)

Resistance by minors will be conducted by the code of conduct accepted by the "Bestuur van de Nederlandse Vereniging voor Kindergeneeskunde" (NVK) at May 21 2001, and it will be specified in the informed consent letter.

9.4 Benefits and risks assessment, group relatedness

In this study we will include (near-)term newborns with proven PAIS. Current treatment options for PAIS mainly focus on controlling convulsions, hypoglycaemia and associated infections. There is no treatment available that leads to reduction of neonatal brain damage in this severely affected group of infants. This leads to life-long consequences of PAIS and forms a large burden for patients and society. The overall aim of this project is to meet this by making the first step towards clinical application of MSCs to treat PAIS. Successful completion of this project will provide the first evidence of the safety and feasibility of intranasally administered bone-marrow derived MSCs in newborn infants with PAIS.

The extra burden of the present study for the included infants is considered to be very limited to non-existent given the fact that besides the nasal treatment to apply the MSCs. treatment is not different compared to the standard acting treatment protocol for newborns with PAIS. Nasal application of MSCs has been considered as non-invasive. With the respect to possible risks of the present MSC treatment, the most important potential risk factors such as inflammatory actions of MSC therapy with allogeneic human MSCs and an increased risk for malignancies, have been intensively investigated in our own preclinical studies and appear to be non-present at long-term follow up. Additionally, human trials on MSC treatment for adult stroke or preterm infants with BPD and other pathologic conditions do not provide evidence for these or other serious adverse events or risks. However, this is the first study administering MSCs intranasally in humans, so potential risks might be unknown and/or unexpected. Using close monitoring and (preventative) planned actions, as described in chapter 11.1e and 11.2, and tightly regulated stopping rules (see chapter 6.7) we expect to minimize or prevent these risks.No single indication has been found in experimental research in the developing animal models that above mentioned complications occur in a higher incidence as compared to non-MSC treated animals, whereas possibility for a substantial better short- and long-term outcome seems very realistic on the basis of previous experimental research data. Therefore we have planned to peform a pilot (phase I/II) trial to assess safety and feasibility of MSC treatment in newborns with PAIS.

9.5 Compensation for injury

The sponsor/investigator has a liability insurance which is in accordance with article 7 of the WMO.

The sponsor (also) has an insurance which is in accordance with the legal requirements in the Netherlands (Article 7 WMO and the Measure regarding Compulsory Insurance for Clinical Research in Humans of 24th November 2014). This insurance provides cover for damage to research subjects through injury or death caused by the study.

The insurance applies to the damage that becomes apparent during the study or within 4 years after the end of the study.

9.6 Incentives (if applicable)

Not applicable.

10. ADMINISTRATIVE ASPECTS, MONITORING AND PUBLICATION

10.1 Handling and storage of data and documents

Data will be handled confidentially (using coding). Where it is necessary to trace data to an individual subject, a subject identification-code list will be used to link the data to the subject. The code will not be based on the patient initials and birth date. The key to the code will be safeguarded by the research team (Principal Investigator), because data and human material will be kept for a longer period of time. The handling of personal data will be complied with the Dutch Personal Data Protection.

10.2 Monitoring and Quality Assurance

A detailed description of monitoring of the study is given in the Monitoringplan and the Monitor proposal (part K6).

10.3 Amendments

A 'substantial amendment' is defined as an amendment to the terms of the METC application, or to the protocol or any other supporting documentation, that is likely to affect to a significant degree:

- the safety or physical or mental integrity of the subjects of the trial;
- the scientific value of the trial;
- the conduct or management of the trial; or
- the quality or safety of any intervention used in the trial.

All substantial amendments will be notified to the METC and to the competent authority.

Non-substantial amendments will not be notified to the accredited METC and the competent authority, but will be recorded and filed by the sponsor.

10.4 Annual progress report

The sponsor/investigator will submit a summary of the progress of the trial to the accredited METC once a year. Information will be provided on the date of inclusion of the first subject, numbers of subjects included and numbers of subjects that have completed the trial, serious adverse events/ serious adverse reactions, other problems, and amendments.

10.5 End of study report

The sponsor will notify the accredited METC and the competent authority of the end of the study within a period of 90 days. The end of the study is defined as the last patient's last visit.

In case the study is ended prematurely, the sponsor will notify the accredited METC and the competent authority within 15 days, including the reasons for the premature termination.

Within one year after the end of the study, the investigator/sponsor will submit a final study report with the results of the study, including any publications/abstracts of the study, to the accredited METC and the Competent Authority.

10.6 Public disclosure and publication policy

There are no specific agreements concerning public disclosure or publication policy.

11. STRUCTURED RISK ANALYSIS

11.1 Potential issues of concern

a. Level of knowledge about mechanism of action

From neonatal rat models of brain injury, we have learned that HI brain injury induces changes in neurovascular environment that promote neurogenesis.(Kadam et al. 2008; Ong et al. 2005; Yang & Levison 2007) However, after HI brain injury, there is no induction and maintenance of long-term neurogenesis. Therefore, it is crucial to assist the brain in regeneration after injury and also to reinforce development of the maturating brain. In animal stroke-model studies, it has been demonstrated that transplantation of murine adult bone marrow-derived MSCs markedly improves neuroregeneration. Treatment with MSC stimulated formation of new neurons and oligodendrocytes and reduced infarct size by >45%. Although intracranial MSC treatment stimulated formation of new brain cells and differentiation of these cells into new neurons and oligodendrocytes, these newly formed cells were not of transplant origin. These findings indicate that the neuroregenerative effect of MSCs after ischemic brain damage mainly relies on stimulation of endogenous repair mechanisms.(van Velthoven et al. 2010c) This is confirmed by other data from our group that show that MSC treatment has profound effects on the expression of growth and differentiation factors in the brain. For example, MSC treatment at 10 days after HI induces upregulation of 35 genes encoding growth and differentiation factors that are mainly involved in cell growth and proliferation. MSC treatment at 3 and 10 days induces expression of 28 additional growth and differentiation factors and these are predominantly involved in cell differentiation and nervous system development.(van Velthoven et al. 2010c; van Velthoven et al. 2011) These results show that the first dose of MSC stimulates cerebral cell proliferation, whereas the second injection enhances differentiation and maturation of newly formed cells and integration in a functional network.(van Velthoven et al. 2010c) Importantly, we have shown recently that at 3 days after MSC administration, the number of MSCs in the brain sharply decreases indicating low survival of MSCs for longer time periods (Donega, 2014 Exp Neurol).

Based on these findings, we hypothesize that MSC of donor origin will only transiently survive in the brain and that the neuroregenerative effects of MSC are mediated predominantly by orchestrating changes in the growth and differentiation factor milieu in the brain. The corticospinal tract is the primary transmission route for voluntary movement of the forepaws. We showed that MSC treatment could also partially restore the damaged

corticospinal motor tract which led to improved sensorimotor outcome.(van Velthoven et al. 2010c; van Velthoven et al. 2010a)

An overview of findings from non-clinical studies on MSC treatment for neonatal stroke is given in chapter 7 of the IB. These studies confirm the role of MSCs in stimulating endogenous neuroregenerative mechanisms and thereby reducing cerebral damage, restoring corticospinal motor tracts and improving sensorimotor outcome.

b. Previous exposure of human beings with the test product(s) and/or products with a similar biological mechanism

At present, there are no results of clinical trials available on the treatment of neonatal stroke with MSCs. The only available trial on MSC administration in neonates, showed that allogeneic hUCB-derived MSC treatment in premature neonates with BPD was safe and without any adverse events. (Chang et al. 2014; Henckel et al. 2015) However, many studies have reported on MSC treatment for stroke in adult patients. An overview of findings from these trials is given in chapter 8 of the IB. In summary, these studies show potential of MSCs in the treatment of adult stroke as they improve functional outcome. Even though neonatal and adult stroke do not have a common underlying cause, they both result in brain damage caused by common harmful processes. These include mechanisms of excitotoxicity and neuroinflammation, involving microglial activation, proinflammatory cytokine production and toll-like receptor (TLR) activation. (Fleiss et al. 2014) Comparable to our study, most of these trials administered MSCs days to weeks after the cerebral damage occurred, while brain tissue loss is usually complete after 10 days.(van Velthoven et al. 2010a; Bonestroo et al. 2015) Therefore the main goal of all MSC treatment studies was not to have neuroprotective effects, but to induce endogenous neuroregeneration and repair. We therefore presume that treatment with MSCs in neonatal stroke will have the same biological mechanism of action as in adult stroke and will also lead to improved neuroimaging and functional outcome.

c. Can the primary or secondary mechanism be induced in animals and/or in ex-vivo human cell material?

An overview of findings from non-clinical studies on MSC treatment for neonatal stroke is given in chapter 7 of the IB. These studies show that MSC treatment in animal models of neonatal stroke reduces cerebral damage, restoring corticospinal motor tracts and improving sensorimotor outcome.

d. Selectivity of the mechanism to target tissue in animals and/or human beings

Human MSCs communicate with other cells in the human body and appear to migrate to areas of injury in response to signals of cellular damage and apoptosis.(Kang et al. 2012; Vogel et al. 2010) MSCs migrate selectively into damaged brain lesions, and specific molecular signals, such as stromal cell- derived factor-1 (SDF-1/CXCR4), intracellular signaling and adhesion molecules (selectins and integrins) and proteases have been reported to be involved in the interaction of MSCs to reach, recognize, and function in cerebral ischemic tissue.(Komatsu et al. 2010; Chavakis et al. 2008; Shen et al. 2007; Shyu et al. 2006) It is therefore hypothesized that areas of brain injury caused by PAIS will attract MSCs to migrate to the ischemic brain injury site. MSCs will be administered intranasally to prevent loss of MSC in peripheral organs (Steiner et al. 2012) and to make sure MSCs will arrive rapidly and efficiently at the injured brain region.

e. Analysis of potential effect

Adverse events

From animal models of neonatal stroke we can conclude that no adverse effects have been described for MSC treatment. Our research group has also assessed long-term safety of intranasal MSC treatment.(Donega et al. 2015) At 14 months following HI no significant lesions or neoplasia were observed in the nasal tubinates, brain or other peripheral organs of mice treated intranasally with MSCs and compared with control or vehicle-treated HI mice. These results provide strong evidence of the long-term safety of MSC treatment following neonatal HI in mice.(Donega et al. 2015)

As MSC treatment has never been studied in human neonatal stroke, we can only provide evidence for the safety of MSC treatment in other pathological conditions. There is only one clinical trial describing the use of MSCs in treatment of neonates.(Chang et al. 2014) Chang et al assessed in a phase I dose-escalation trial the safety and feasibility of intratracheal administration of allogeneic umbilical cord-derived MSCs in preterm infants with high risk for BPD. Nine infants were included in this study: 3 patients were given 1 x 10^7 MSCs/kg and 6 patients were given 2 x 10^7 MSCs/kg. After 7 days there was a decrease in inflammatory cytokines (e.g. interleukin-6 and interleukin-8) and BPD severity was lower in patients who received MSCs compared to their historical case-matched controls. Importantly, there were no serious adverse events or toxicity related to a higher dose.(Chang et al. 2014) More recently some preliminary findings from another trial were published, confirming safety and feasibility of MSC treatment in premature BPD

patients.(Henckel et al. 2015) Although these MSCs were administered intravenously, no adverse effects were found.(Henckel et al. 2015)

As described in chapter 8 of the IB, there are many other clinical trials in adults in which MSC are used for the treatment of several diseases. Although the hypothesized mode of action of MSCs in different pathological conditions varies, the most important findings from these clinical trials refer to safety issues. In none of the trials serious adverse events related to MSC treatment were detected during bone marrow harvesting and administration. Some studies reported mild allergic reaction(Duijvestein et al. 2010), probably related to preservation substances in the MSC-product, or self-limiting fever within a few hours after MSC-transplantation. (Shi et al. 2012) In some studies patients had a serious adverse event, most likely not related to MSC administration. (Forbes et al. 2014; Wang et al. 2013; Weiss et al. 2013; Haack-sørensen et al. 2014) Additionally, a large meta-analysis on clinical trials for numerous diseases did not show any evidence for severe adverse effects due to MSC transplantation.(Lalu et al. 2012) This analysis used both adult and pediatric trials to report on a total of 1012 patients with ischemic stroke, Crohn's disease, cardiomyopathy, myocardial infarction, GvHD and healthy volunteers. Including eight randomized control trials, there was no association detected between MSC transplantation and acute infusional toxicity, organ system complications, infection, death or malignancy. There was a significant increase in fever with MSCs compared to the control group, but the fever was reported to be transient in all trials and most often low grade (≤38°C).(Lalu et al. 2012)

No correlation between the dose of MSC and their potential efficacy or side effects could be observed in multiple studies (range 1-8 10^6 cells/kg body weight).(Lalu et al. 2012) It is known that systemic complications such as fever are more common when MSCs were systemically (e.g. intravenously) administered. We found no evidence that fever occurred in our animal studies.(Donega et al. 2015) From our preclinical studies in mice we found that local (intracranial) administration of MSCs at 3 days after brain injury resulted in a decrease of pro-inflammatory cytokines IL-1 β , IL-1R and IL-3.(van Velthoven et al. 2011)In vitro we have also found that if MSCs are cultured in a hypoxic-ischemic brain environment, they produce more growth factors and less pro-inflammatory cytokines (IL-1 β , IL-6 en TGFb) than MSCs cultured in a normal brain environment.(van Velthoven et al. 2010b) Intranasal administration of MSCs, dampened neuro-inflammatory responses due to hypoxic-ischemic brain injury at 5-18 days after MSC treatment. The number of GFAP and Iba-1 positive cells, as markers for the neuroinflammatory response of glial cells, decreases after administration of MSCs, possibly as a result of anti-inflammatory

functions of MSCs. (Donega, Nijboer, van Tilborg, et al. 2014) In conclusion, it seems that local/nasal MSC treatment has rather an anti-inflammatory effect and will not induce inflammation. We therefore do not expect fever to complicate intranasal administration of MSCs, as a priori chances are low. Additionally, the danger of transient and low grade fever is low.

With respect to possible risks of the present MSC treatment, the most important potential risk factors such as inflammatory actions of MSC therapy with allogeneic human MSCs and an increased risk for malignancies, are intensively investigated in our own preclinical studies and were not found. (Donega et al. 2015) In addition, we found that intranasal administration of human MSCs enhanced secretion of anti-inflammatory cytokines.(Donega, Nijboer, Braccioli, et al. 2014) Additionally, human trials on MSC treatment for adult stroke or other pathologic conditions do not provide evidence for these or other serious adverse events or risks. No single indication has been found in experimental research in the developing animal models that above mentioned complications occur in a higher incidence as compared to non-MSC treated animals, whereas possibility for a substantial better short- and long-term outcome seems very realistic on the basis of previous experimental research data. However, this is the first study administering MSCs intranasally in humans, so potential risks might be unknown and/or unexpected. Therefore, we have planned to perform a pilot (phase I/II) trial to assess safety and feasibility of MSC treatment in newborns with PAIS. Using close monitoring and (preventative) planned actions, as described in chapter 11.1e and 11.2, and tightly regulated stopping rules (see chapter 6.7) we expect to minimize or prevent these risks.

Summary of potential risks

Even though there is no evidence that risks as mentioned below occur in a higher incidence as compared to non-MSC treated animals, these risks will be monitored as part of standard clinical care on the NICU. These risks are based on theoretical mechanisms of action, most likely to occur after systemic administration of MSCs. In general, risks or adverse events related to MSC treatment can be categorized in three groups: acute, subacute and longterm adverse effects.

- 1. Acute adverse effects: Administration Reaction/Toxicity
 - Systolic blood pressure >33% decrease or increase from the baseline during or directly following the intranasal administration of the investigational product

- Diastolic blood pressure >25% decrease or increase from baseline during or directly following the intranasal administration of the investigational product
- Heart rate >33% decrease or increase from baseline during or directly following the infusion of the investigational product
- Development of dyspnoea, vomiting, flushing, diarrhea, during or within 1 hour from the intranasal administration of the investigational product
- Fever ≥ 2 grade increase from baseline during or within 2 hours from the intranasal administration of the investigational product
- Development of exanthema, or urticaria developing during or within 2 hours from the intranasal administration of the investigational product
- 2. Subactue adverse effects:
 - Bacteremia due to bacterial contamination of product. Fever ≥ 2 grade increase from baseline during or within 2 hours from the intranasal administration of the investigational product AND product contamination proven by positive product cultures. In case of contamination patients will be treated with antibiotics in case this is required.
 - Systemic infection (e.g. meningitis) due to use of MSCs. We have no evidence from preclinical trials, nor from trials in adult stroke or neonatal BPD, that MSC treatment increases the risk of infections. However, MSCs might be able to change inflammatory status. In order to monitor more closely, we will take extra blood samples from all subjects at baseline and 24 hours following MSC administration to determine infection markers such as CRP, procalcitonine and complete blood count.
 - Post-administration virus infection. This risk is minimal and adherent to all blood (derived) product administration. If a patient develops a new viral infection that is suspected to be due to transfusion of blood products or intranasal administration of the investigational product, a lookback procedure should be initiated by the treating physician according to local regulations for all blood products received. If a MSC donor is proven to be the source of virus infection, this shall be considered a serious adverse event. All donors are being screened for infectious disease markers as indicated by the Wet Veiligheid en Kwaliteit Lichaamsmaterialen (WVKL), the transposition into Dutch Law of the EU Directive 2006/17. Please find specification of control of drug stubstance in chapter 2.1.S.4.1 of the IMPD.
- 3. Long-term effects: Ectopic tissue formation and tumorigenicity

Although concerns that MSCs might transform into tumorigenic cells still exist, there is a general agreement that bone-marrow-derived MSCs can be safely

